1 ABREVIATIONS

ADL	Activities of Daily Living
AE	Adverse event
GDS	GeriatricDepresionScale
FC	Fried's Criteria
EC	Ethics Committee
eCRF	Case Report Form
GCP	Good Clinical Practice
EQ-5D	EuroQolfive-dimensional (EQ-5D)
CRO	Contract Research Organization
IADL	Instrumental Activities of Daily Living
INE	Instituto Nacional de Estadística (Spain)
ICF	InformedConsentForm
MMSE	Minimental State Examination
SPPB	Short Physical Performance Battery
PASE	Physical Activity Scale for the Elderly
CAM	Confusion Assessment Method
ICER	Incremental cost-effectiveness ratio
PI	Principal Investigator
HUG-GRT	Hospital Universitario de Getafe-Servicio de Geriatría

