4 OUTCOMES

4.1 PRIMARY OUTCOMES:

1. **Disability:** It was measured by the Barthel Index for basic Activities of Daily Living and the Lawton index for instrumental activities of daily living.
2. **Functional status and performance-based measures:** Functional status and performance-based measures: Is measured by Short Physical Performance Battery (SPPB), Physical Activity Scale for the Elderly (PASE SCALE).
3. **Quality of Life:** Quality of life was assessed by self-reported questionnaire EuroQL 5D 5L. It will be measured during admission to hospital and follow-up.
4. **Geriatrician Intervention:** The impact of their intervention is measured by quantifying in a register any additional tests requested and medical advice by other specialists.

4.2 SECONDARY OUTCOMES:

Prevalence of Delirium: The delirium cases are detected by Confusion Assessment Method (CAM) scale.

Cognitive Impairment: Will be measured by the Mini Mental State Examination (MMSE) in the initial assessment.

Depression: will be assessed using the Geriatric Depression Scale in the baseline assessment.

Health-care associated infections: Acquired during hospitalization start.

Geriatric Syndromes: The geriatric evaluation including the following aspects: clinical, functional, mental and social.

Comorbidity: Will measured at initial assessment thorough Charlson index

Nutritional Status: Will measured at initial assessment thorough the Mini Nutritional Assessment and body Mass index.

Polypharmacy: Defined as five or more prescription drugs.

Mortality rate: Number of deaths during follow-up. It is calculated using official report of the National Statistics Institute (INE).

Average stay hospitalization: Average length of stay of stay all discharges. We will obtain from Hospital Admissions service.

Hospitalization Rate in Emergency room: Number of hospital admissions over the total of patients admitted in the hospital.

Readmission rates: Number of readmissions during of follow-up period. I will get the data in Hospital Admissions Service.

Institutionalization: Number of patients referred to nursing home after discharge or at any time during follow-up. This information is obtained directly from patients or their relatives.

Requirement of caregiver: Number of patients who require a caregiver after hospital discharge.

Caregiver burden: Will be used Zarit Scale for assessing caregiver burden

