5 STUDY DESIGN

This trial is designed as a randomised, multicenter, phase III trial to evaluate the feasibility and viability of clinical and therapeutic approach frail older people in high risk clinical settings (Emergency room, General Surgery, Oncology, Cardiology, and Nephrology). Patients will be randomized on a 1:1 basis to receive either usual treatment or usual treatment plus geriatric interventions.

The patients will be recruitment in Spain, Italy and United Kingdom. In Spain will be included the following centres: Hospital Universitario de Getafe (Madrid), Hospital Universitario Central de Asturias Monte Naranco (Asturias); In Italy: Ospedale San Raffaele (Rome), Universitat Cattolica del Sacro Cuore (Roma), in United Kingdom: (Cardiff University and other one to be determined) According to feasibility in each centre will be recruitment patients from differents clinical settings. See Table No 1

Table 1. Recruitment distribution of patients according to hospital and setting

Hospital	Setting
Hospital Universitario de Getafe. (Madrid - Spain)	Emergency room Cardiology ward Elective Surgery Emergency Surgery
Hospital Universitario Monte Naranco. (Asturias - Spain)	Oncology Elective Surgery Emergency Surgery
[name] (England – United Kingdom)	Emergency room Cardiology Ward Elective Surgery
Cardiff University (Wales - Reino Unido)	Emergency room Nephrology ward Elective Surgery
Ospedale San Raffaele (Rome - Italy)	Cardiology Ward
Universita' Cattolica del Sacro Cuore (Rome - Italy)	Emergency Room Cardiology Ward Elective Surgery

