7.4 STATISTICAL ANALYSIS

Firstly, subject's basal characteristics at recruitment will be analyzed. Descriptive statistics of epidemiological and clinical data will be calculated (described in section 9). This analysis will be done in a conjoint manner, according to treatment and clinical setting (emergency room, general surgery, oncology, cardiology, and nephrology).

To verify the differences between the arms of the study a Mann-Whitney test will be made. Based on the inclusion criteria, it is expected that the differences will be produced by the intervention, and not because of differences between groups.

[figure not shown]
To evaluate the intervention in each clinical setting, the effect of the intervention and its statistical significance will be determined.

These effects shall be broken down into two classes depending on the event. First the prevalence rate, and in case the event's duration could be assessed, evaluate if this duration has changed..

For each outcome described in section 4, comparisons between predictive values of the logistic models for each scale will be made in order to determine which scale is optimal in a global manner, according to clinical setting.

In case the date of death and hospitalization can be obtained, survival models will be done.

Diagram 1. Flowchart of randomized clinical trial

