9.2 EVALUATION AT DISCHARGE FROM THE SPECIFIC CLINICAL SETTING

The following aspects will be assessed:

- Mortality
- Frailty assessment with L. P. Fried's scale and/or FRAIL scale. Functionality assessment with Barthel Index. Indicate the number of hospital stay in days .
- Describe if the patient change the Ward location/ medical /surgical in the hospital (UCI, Coronary unitetc) o)during the evolution in the hospital
- Quantification the number of test (Blood test, urine test, X- Ray, ecography, CT, etc and more specialized like: PET TAC, echocardiography, polisomnography, etc.)
- Quantification the number of consult with other specialist, social worker, palliative care. Etc.
- Usual treatment (Register all the medication at discharge
- Evaluate if the patient develop geriatric síndrome (page 22).
- Destination at dischargeia. (Nursing home, follow up by home care team, I HUG- GRT, day hospital, rehabilitation at home , specialist consultation, etc.)
- Evaluate the perception of the quality of life with the scale EuroQol five-dimensional (EQ-5D).
- Burden of the caregiver with the Economics questionnaire s.
- Economics evaluation Index 3

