9.3 EVALUATION AT 3 MONTHS OF DISCHARGE

Re-evaluate the following aspects by phone :

- Mortality
- Functionality data (Barthel index , Lawton index , PASE Scale).
- Usual medication.
- Residency at the moment.
- Frailty with the FRAIL scale..
- Data of quality of life with the scale EuroQolfive-dimensional (EQ-5D)
- Number of hospitalization and ER, indicate the cause (diagnosis)
- Caregiver burden with the economic questionaries .
- Economics evaluation, Index 3

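### Section 4.2 takes mortality from the Spanish statistics institute in a three-country trial and is not reconciled with the death records that section 9 collects in every centre

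*Combined protocol and SAP*

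**What the plan says.** Section 4.2 lists, among the secondary outcomes, "Mortality rate: Number of deaths during follow-up", and continues: "It is calculated using official report of the National Statistics Institute (INE"). No other source is named there. Section 1 expands the abbreviation as "Instituto Nacional de Estadística (Spain"), so it cannot be read as each country's own institute.

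Section 5 states that "The patients will be recruitment in Spain, Italy and United Kingdom". Table 1 lists two centres in Spain, two in Italy and two in the UK.

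Section 9 collects death separately. Mortality is the first item under "9.2 EVALUATION AT DISCHARGE FROM THE SPECIFIC CLINICAL SETTING". It is also the first item of the 3-month and 12-month assessments in sections 9.3 and 9.4, which are introduced with "Re-evaluate the following aspects by phone". The Death row of Table 2 is marked at the same three points. None of this is limited to Spain.

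On dates, section 7.4 says only: "In case the date of death and hospitalization can be obtained, survival models will be done".

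**The concern.** The outcome definition names a source that can cover only the Spanish patients, while the visit schedule gathers the same information everywhere. An analyst who follows section 4.2 would set aside death data already collected at four centres. An analyst who combines the two sources has no rule for doing so.

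This matters because country and setting are tied together. In Table 1, nephrology is recruited only at Cardiff, while oncology and emergency surgery are recruited only in Spain. Section 7.4 evaluates the intervention setting by setting, and section 7.3 foresees a meta-analysis across settings. A source that varies by country would therefore appear as a difference between settings. Section 10 also uses the survival rate in a parallel cost-effectiveness analysis and survival time in the QALYs, so the problem reaches beyond one line of the secondary outcomes.

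**Working it through.** The plan states no expected mortality, so there is no figure of its own to reproduce. The check has five steps.

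**1. Count centres and cells in Table 1.** Spain: Getafe 4 settings, Asturias 3, total 7. Outside Spain: England 3, Cardiff 3, the two Rome centres 1 and 3, total 10. So 4/6 = 67% of centres and 10/17 = 59% of cells are outside Spain.

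**2. Share of deaths that INE could cover on a literal reading.** If mortality is equal across countries, this share equals the Spanish share of patients. The plan gives no recruitment by centre, so three assumed splits are shown.

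- By centre: 2/6 = 33%.
- By cell: 7/17 = 41%.
- By setting, with 310 patients each and centres sharing equally. The stated total implies 1860/310 = 6 settings, which fits Table 1 if elective and emergency surgery are counted separately:

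| Setting | Spanish centres / all centres | Spanish patients |
|---|---|---|
| Emergency room | 1/4 | 77.5 |
| Cardiology | 1/4 | 77.5 |
| Elective surgery | 2/5 | 124 |
| Emergency surgery | 2/2 | 310 |
| Oncology | 1/1 | 310 |
| Nephrology | 0/1 | 0 |
| Total | | 899 |

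899/1860 = 48%. Section 7.3 names only five settings. With surgery as one setting shared by five centres, two of them Spanish, the result is (77.5 + 77.5 + 124 + 310 + 0)/(5 × 310) = 589/1550 = 38%, which lies inside the same range.

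The 0% for nephrology and the 100% for oncology and emergency surgery do not depend on how patients are split.

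**3. Effect on the reported rate (literal reading).** Apparent rate = true rate × share covered, over all randomised patients. The true rates are assumptions:

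- 10%: 3.3% to 4.8%
- 20%: 6.7% to 9.7%
- 30%: 10.0% to 14.5%

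**4. If section 9 records are combined with INE.** Let L be the proportion not reached at the contacts. Suppose those patients die at the same rate as the others, and INE can be matched to individuals (the plan does not describe this). Capture is then 1 − L outside Spain and up to 1 in Spain. Taking L from 0 up to the 20% drop-out assumed in section 7.3, a true 20% would read between 20% and 0.20 × 0.80 = 16% in Italy and the UK, against 20% in Spain. Deaths in hospital would be known whatever the phone contact, which narrows the gap. Higher mortality among patients not reached would widen it.

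**5. Effect on the treatment comparison.** If a fraction s of deaths is captured in both arms, the observed risk ratio is (s·p1)/(s·p0) = p1/p0, which is unchanged. The observed risk difference is s·(p1 − p0). On the literal reading it shrinks to 33% to 48% of its true size overall, and precision falls with the number of events.

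**The case against.** The strongest reply is that section 4.2 does not exclude the section 9 records. It defines the outcome as deaths during follow-up, and the discharge, 3-month and 12-month contacts are that follow-up. A sensible analyst would use them, and the INE sentence would become a supplementary check for Spain. This stands in part. A reader might infer that deaths in Italy and the UK will be missed; the documents do not support that, because they schedule death collection in every centre. The loss in steps 2 and 3 arises only if INE is the sole source. What survives is that INE is the only source section 4.2 names, with no order of precedence.

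A reader might also infer that the randomised comparison is biased. Allocation is 1:1 within a common protocol, and nothing suggests that INE would capture deaths differently by arm. Step 5 shows that equal under-capture leaves the within-setting risk ratio intact. The contrast between nephrology and oncology is not a randomised one.

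Finally, a single loss figure would be misleading. The result moves from 33% to 48% with the recruitment split. The yearly mortality percentages beside the Charlson index in Appendix 2 are generic values for that score, not planning assumptions for this trial.

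**Conclusion.** The inconsistency is certain from the text: a Spanish source is named for a three-country outcome, and it is not reconciled with the schedule of death records. The size of the consequence is conditional. On an INE-only reading about 33% to 48% of deaths would be counted, assuming equal mortality across countries and one of the recruitment splits above, with none counted in nephrology. If section 9 records are used as well, most of that loss need not occur. Ascertainment would still differ by country and therefore by setting, since only Spanish patients lost to phone contact have a named register behind them. Rates, risk differences and between-setting comparisons of a secondary outcome are exposed; the within-setting risk ratio is not biased by this alone. The point should be corrected, but it does not threaten the primary outcomes.

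**What to change.** Replace the INE sentence in section 4.2 with a definition that applies to every centre: death from any cause among all randomised patients, taken from hospital records and the scheduled discharge and follow-up contacts, with the date of death recorded. Where a national source is available, use it to supplement patients who could not be reached, and state the order of precedence when sources disagree. National sources should not be limited to confirming known deaths, because patients not reached by phone are those for whom a register helps most. Add a sensitivity analysis that uses only the source common to all centres.

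Before the endpoint is fixed, reconcile the follow-up window: section 7.2 gives the third and sixth month after discharge, whereas sections 9.3 to 9.5 and Table 2 give 3 and 12 months. A recorded date of death would also remove part of the condition that section 7.4 places on the survival models.

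The cost is some wording, one additional analysis and one date field if the eCRF lacks it; the eCRF is not in the documents, so this cannot be checked. The contacts are already scheduled.

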3 OBJECTIVES

3.1 PRIMARY OBJECTIVE:

To assess the feasibility and effectiveness of programs designed to detect and manage frail older patients in high risk clinical settings, and to avoid functional impairment and other associated adverse outcomes. These high risk settings will be medical wards (cardiology, oncology or nephrology), major surgery wards and Emergency rooms.

3.2 SECONDARY OBJECTIVES:

- Determine the feasibility of implementing clinical and therapeutic approach to geriatric physician in elderly patients in high risk clinical settings
- Determine disability by evaluating basic and instrumental activities of daily living in frail elderly patients treated in high risk clinical settings.
- Establish functional status in frail elderly people seen in high risk clinical settings.
- Evaluate quality of life through an instrument validated in frail patients seen in high risk clinical settings.
- Establish mortality ratio in frail patients included in high risk clinical settings.
- Obtain the rate of re-hospitalization in frail patients seen in high risk clinical settings.
- Determine the average stay of hospitalization in frail elderly patients treated in high risk clinical settings.
- Obtain the rate readmission to emergency room and hospitalization in frail older patients treated in high risk settings.
- Determine the average stay of hospitalization in frail elderly patients treated in high risk clinical settings.
- Determine the rate of delirium in frail elderly patients in high risk settings.
- Obtain the rate of health-care associated infections in frail older patients seen in high risk settings.
- Determine the rate of polypharmacy in frail older patients seen in high risk settings.
- Establish the secondary institutionalization rate accordingly to decline the functional status in frail elderly patients in high risk settings.

- Determine the need for a caregiver as a result of decline the functional status in frail older people in high risk settings.
- Establish the caregiver burden in hospitalized frail patients on high risk settings.
- Establish the secondary institutionalization rate accordingly to decline the functional status in frail elderly patients in high risk settings.
- Determine the need for a caregiver as a result of decline the functional status in frail older people in high risk settings.
- Establish caregiver burden of frail elderly patients seen in high risk settings.

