Complementing the main cost-effectiveness analysis, we will develop several parallel cost effectiveness analysis to the extent that effective change. The results that we will use are: hospitalization rate and readmission, lenght of hospitalization and in the Emergency department, episodes of delirium and nosocomial infection, post-surgical complications as a whole and by surgical procedure, number of inappropriate drugs, adherence to treatment, permanent institutionalization rate, survival rate, preventable side effects due to under / over / mismanagement on caregiver burden.

Cost-utility analysis:

Cost-utility analysis (ACU) is an evolution of cost-effectiveness analysis, in which the interference effects are measured in a unit that synthesizes the lifespan and quality of life. The best and better known measure is the quality of life-adjusted per quality (QALY QALY or in its Anglo-Saxon sense). The QALYs are calculated by weighting the survival time (years of age) with quality adjustment thereof, called utility, which represents the preference values in relation to different health states (reference). For the purpose, the EQ-5D-5L instrument will be used. The incremental cost-utility relation answers the following expression:

$$\text{ACU}_{\text{incremental}} = (C_a - C_b) / (\text{AVAC}(a) - \text{AVAC}(b))$$

Statistical analysis:

A descriptive analysis of the main resources used in health care, social services and informal care will be performed.

This includes basic statistics such as means, medians, standard deviations, skewness, kurtosis, ranges, bivariate analysis using different cost elements and individual characteristics (sex, age,...) and health outcomes.

Because different distributions are expected from major cost components, we hope to develop different multivariate estimation methods. As we expect a non-normal distribution of the estimated costs, an alternative analysis would be the use of GLM models grouped by clusters, where depending on the distribution of the estimated costs (distribution Gamma, Poisson or Gaussian), will be used the most suitable method of empirical analysis. Another alternative, if the necessary information is obtained, could be an analysis using multilevel models of 2 or 3 grade (Recital country and center). The costs

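### Readmissions are a raw count with no time alive at risk and no rule for death, and length of stay has no settled unit (all discharges or index stay)

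*Combined protocol and SAP*

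**What the plan says.** Section 4.2 lists both outcomes as secondary. Stay is "Average length of stay of stay all discharges", taken from the hospital admissions service. For readmission the text is: "Readmission rates: Number of readmissions during of follow-up period. I will get the data in Hospital Admissions Service". Mortality is a separate raw count, "Number of deaths during follow-up". The neighbouring outcome, hospitalisation from the emergency room, is given a denominator; readmission is not, although section 3.2 calls it a rate: "Obtain the rate readmission to emergency room and hospitalization in frail older patients treated in high risk settings".

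The data collection is narrower than these definitions. At the discharge evaluation (section 9.2) the instruction is "Indicate the number of hospital stay in days", and Table 2 marks hospital stay at discharge only. The later telephone contacts (sections 9.3 and 9.4) ask for "Number of hospitalization and ER, indicate the cause (diagnosis"). Neither dates nor lengths of those admissions are listed.

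Section 7.4 plans survival models if dates of death and hospitalisation can be obtained. It names no method for recurrent events or competing risks. Section 7.2 puts the post-discharge follow-up at 3 and 6 months; sections 9.3 to 9.5 and Table 2 put it at 3 and 12 months. Section 10 uses "hospitalization rate and readmission, lenght of hospitalization and in the Emergency department" among the effect measures of its complementary cost-effectiveness analyses.

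**The concern.** The patients are over 75 and frail, so deaths during follow-up must be expected, and the trial aims to avoid adverse outcomes. A patient who has died cannot be readmitted. A count that ignores time alive therefore credits the arm with more deaths with fewer readmissions.

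The stay outcome has a different weakness. Taken literally, its unit is the discharge, and the number of discharges depends on readmissions, which the intervention may change. Taken as the index stay, it is free of that problem, but a death in hospital ends the stay, so early deaths can shorten the mean, and no rule covers them. Two analysts following the text could report different outcomes.

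At stake are the size, and for small effects the sign, of two secondary comparisons and of the complementary cost-effectiveness ratios that use them.

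**Working it through.** The documents give no readmission rate and no length of stay, so there is no planned figure to reproduce. All sizes below are illustrations on stated assumptions.

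**Readmissions.** Assume the same readmission rate per year alive in both arms, a constant death hazard and a 12-month window. With 12-month mortality m, mean years alive per patient are m / (−ln(1 − m)). The values 12%, 26% and 52% are annual figures printed beside the Charlson index in Appendix 2; 20% and 30% are assumed.

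- m = 12%: 0.12 / 0.1278 = 0.939
- m = 20%: 0.20 / 0.2231 = 0.896
- m = 26%: 0.26 / 0.3011 = 0.863
- m = 30%: 0.30 / 0.3567 = 0.841
- m = 52%: 0.52 / 0.7340 = 0.708

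The count ratio (lower-mortality arm over the other) is the ratio of years alive. Its inverse is the true rate ratio that would appear as equal counts.

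| Mortality, higher vs lower | Count ratio at equal rates | True rate ratio hidden as equal |
|---|---|---|
| 26% vs 20% | 1.04 | 0.96 |
| 30% vs 20% | 1.07 | 0.94 |
| 26% vs 12% | 1.09 | 0.92 |
| 52% vs 26% (extreme) | 1.22 | 0.82 |

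In numbers: with 155 per arm (section 7.3, one setting) and an assumed 0.8 readmissions per year alive, 26% versus 20% mortality gives 155 × 0.8 × 0.863 ≈ 107 against 155 × 0.8 × 0.896 ≈ 111, with no true difference.

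Two simple denominators do not repair this. Dividing by the number randomised leaves the ratio at 1.04, because allocation is 1:1. Dividing by 12-month survivors errs the other way: 0.8 × 0.863 / 0.74 = 0.933 against 0.8 × 0.896 / 0.80 = 0.896. Only time alive gives 0.8 in both arms.

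For a large effect, halve the rate at 30% versus 20% mortality: the count ratio is 0.5 × 1.066 = 0.53, still clearly favourable.

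**Length of stay.** Let I be the index stay, L the readmission stay and r the readmissions per patient, all assumed. The mean per discharge is (I + rL) / (1 + r); days per randomised patient are I + rL. Let the intervention cut r from 0.6 to 0.3.

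| I, L (days) | Mean per discharge | Days per patient |
|---|---|---|
| 8, 4 | 6.50 to 7.08 | 10.40 to 9.20 |
| 8, 6 | 7.25 to 7.54 | 11.60 to 9.80 |
| 10, 4 | 7.75 to 8.62 | 12.40 to 11.20 |
| 8, 12 | 9.50 to 8.92 | 15.20 to 11.60 |

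The mean per discharge is a weighted average of I and L, so preventing readmissions raises it only when L is below I. With I of 8 or 10, L of 4 or 6, and r cut from 0.6 to 0.3 or from 0.4 to 0.2, the rise is 0.24 to 0.87 days while days per patient fall by 0.8 to 1.8. If only index discharges count, the mean is I in both arms and the change is zero.

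**The case against.** The strongest reply on stay is that the data collection points to the index stay: section 9.2 and Table 2 record it once, at discharge, and no later contact asks for the length of an admission. On that reading preventing readmissions cannot move the average. This stands. A reader might infer from section 4.2 that the average stay will lengthen when the intervention works; the documents do not support that as a fact. It needs readmission discharges to be included and to be shorter than the index stay, and the documents give no lengths. What remains is an outcome definition that does not match its data collection, and no rule for deaths in hospital.

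On readmissions, the reply is that the distortion is modest and that section 7.4 foresees survival models. The first part stands: the sign changes only when the true rate reduction is smaller than the survival effect, about 4% to 8% in the three cases that exclude the extreme row. The second part helps only partly. The models depend on dates that sections 9.3 and 9.4 do not list, and nothing says how repeated readmissions or death would enter.

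A reader might also infer that the admissions service sees only the study hospital. The documents do not describe its coverage. They do name two sources, the service and the telephone contacts, without saying how to combine them.

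Finally, the main cost-effectiveness analysis in section 10 uses functional status, so this point does not reach it.

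**Conclusion.** The point holds in a limited form. The readmission outcome as defined is biased against the arm with better survival, by about 4% to 9% for 12-month mortality gaps of 6 to 14 percentage points, assuming a constant hazard and equal readmission rates while alive. This can mask or reverse a small benefit. A reader might go further and conclude that the count generally moves the wrong way when the intervention works, or that readmissions should be divided by patients still alive. The first fails for any sizeable effect, and the second replaces one bias with another. The missing element is time alive.

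For stay, the finding is an unresolved unit: sections 4.2 and 9.2 must be reconciled, and the direction of any distortion cannot be known from the documents. The change is worth making because it is cheap, but it concerns two secondary outcomes and the complementary economic analyses only.

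**What to change.** 1. Define stay as the index stay in days per randomised patient, from section 9.2, and report deaths in hospital separately by arm.
2. Analyse readmissions per randomised patient with a rate regression that uses the log of days alive and under follow-up as offset, not a division by survivors. Patients who die during the index stay contribute no time after discharge, so show them beside the result, and read the rate together with mortality. As a supporting analysis, use time to first readmission with death as a competing event.
3. State one rule for combining admissions-service records with telephone reports, for example that an admission counts if either source shows it. Record dates of admission and death at the existing contacts.
4. Use one follow-up window, after reconciling section 7.2 (3 and 6 months) with sections 9.3 to 9.5 (3 and 12 months).

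Days alive and out of hospital per randomised patient is a useful option but not necessary; it would also need discharge dates for each readmission.

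The cost is revised outcome wording, date fields at two existing calls and slightly more analysis. Self-reported admissions and their dates will be less precise than hospital records. The mortality source named in section 4.2 is the Spanish statistics institute, so the Italian and UK sites need a stated source for dates of death.

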7.3 SAMPLE SIZE

Dependence and disability affects quality of life perception and increases health costs. Hence, this variable will be taken to calculate sample size. According to literature, the incidence of disability in frail older people is approximately 40%.

In order to avoid the estimation bias, the sample size will have at least 10 outcomes as variables. Therefore, the formula has been calculated for a 95% confidence interval to obtain at least 40 events.

$$n * p \pm z_{1-\frac{\alpha}{2}} \sqrt{n * p * (1-p)}$$

It has been assumed drop-out rate of 20% and an incidence of disability described above. Hence, the sample size should be at least 1860 participants. In each clinical setting (emergency room, general surgery, oncology, cardiology and nephrology) 310 participants should be evaluated (155 in each group: control and intervention).

In case of not obtaining the minimal sample size in each clinical setting, the pondeate models will be made. Additionally, a meta-analysis will be performed including the global effect of the intervention according to clinical setting and with a thorough sensitivity analysis.

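### Section 4.2 divides emergency-room admissions by patients admitted: counted once per patient the rate is 1 in both arms, and no reading gives the admission risk among randomised participants

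*Combined protocol and SAP*

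**What the plan says.** Section 4.2 lists a hospitalisation rate for the emergency room and defines it as "Number of hospital admissions over the total of patients admitted in the hospital". Repeat admissions have their own entry in the same list: "Readmission rates: Number of readmissions during of follow-up period".

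The emergency room is one of the recruitment settings. Section 5 lists "high risk clinical settings (Emergency room, General Surgery, Oncology, Cardiology, and Nephrology", and four of the six centres in Table 1 recruit there. Allocation is individual: "Patients will be randomized on a 1:1 basis to receive either usual treatment or usual treatment plus geriatric interventions". Section 7.3 plans, for each setting, "310 participants should be evaluated (155 in each group: control and intervention".

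No other section supplies a different denominator. Section 7.4 says the effect will be determined within each clinical setting but does not restate the rate. The visit lists in 9.2 to 9.4 and the schedule in Table 2 name items to collect without defining it. Section 10 lists hospitalisation rate among the effects for the parallel cost-effectiveness analyses, also without a denominator.

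**The concern.** A hospitalisation rate should tell the reader what proportion of the patients at risk were admitted. Here the people who can supply the numerator are exactly the people in the denominator. Someone seen in the emergency room and sent home appears in neither, so a fall in admissions shrinks both terms together.

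At stake is the only outcome in section 4 that is specific to the emergency room. As worded it cannot show whether the geriatric team changes the chance of admission from that setting. If the same definition were carried into section 10, the difference in effect would be 0 and the incremental cost-effectiveness ratio, which divides by that difference, would be undefined. Section 10 does not say which definition it uses, so this second consequence is conditional.

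**Working it through.** **Plan's own figures.** The plan states no expected value, effect size or power for this outcome. The only design figure used here is the 155 per arm in section 7.3. That figure can be roughly recovered. The smallest n with 0.4n − 1.96·√(0.24n) ≥ 40 is 128 (51.2 − 10.86 = 40.34), and 128 × 1.2 = 153.6, or 154. The point about the denominator does not depend on it.

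**Inputs.** N = 155 per arm (section 7.3). Numerator and denominator as worded in section 4.2. Admission risks are assumptions, shown as two pairs: 40% versus 30%, and 60% versus 45% (control versus intervention).

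**Reading 1: each patient counted once.** Let A be the number of patients admitted in an arm. The written rate is A/A = 1; with the randomised denominator it is A/N.

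| Assumed risks | Admitted (A) | As written | Over randomised | Difference as written | Difference over randomised |
|---|---|---|---|---|---|
| 40% vs 30% | 62 vs 46 | 62/62 vs 46/46 | 40.0% vs 29.7% | 0 | 10.3 points |
| 60% vs 45% | 93 vs 70 | 93/93 vs 70/70 | 60.0% vs 45.2% | 0 | 14.8 points |

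The zero is algebraic and holds for any pair of risks.

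**Reading 2: repeat admissions counted.** The rate is (A + R)/A = 1 + R/A, where R is the number of readmissions. For an assumed 0.1 to 0.3 readmissions per admitted patient it is 1.1 to 1.3. This can differ between arms, but it measures readmission, which section 4.2 already lists. For participants randomised before the admission decision, it also conditions on a post-randomisation event that the intervention may change.

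**Reading 3: all admissions to the hospital as denominator.** This brings in people who are not in the trial, so it is not a comparison of randomised groups.

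**Reading 4: emergency-room admissions as a share of all trial admissions in the arm.** Assume four other settings of 155 per arm, all inpatients. Then 40% versus 30% gives 62/(62 + 620) = 9.1% versus 46.5/(46.5 + 620) = 7.0%. The arms differ, but the value depends mainly on how recruitment is spread over settings.

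None of the four is the risk of admission among participants randomised in the emergency room.

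**What the randomised denominator would deliver.** Using the two-proportion normal approximation, power = Φ{[δ√N − 1.96·√(2p̄(1−p̄))] / √(p₁(1−p₁) + p₂(1−p₂))}, where δ is the risk difference, p₁ and p₂ are the two risks and p̄ is their mean. With N = 155:

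- 40% vs 30%: (1.245 − 1.322)/0.671 = −0.115, power about 45%.
- 60% vs 45%: (1.867 − 1.384)/0.698 = 0.692, power about 76%.

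The correction makes the outcome interpretable, but not well powered.

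**The case against.** The strongest reply is that this is a drafting or translation slip. The document is in rough English with Spanish left in places, and the outcome's label points to patients seen in the emergency room. An analyst would hardly compute 62/62. That is probably true, and it argues against expecting a guaranteed null result. It does not supply a denominator, and leaving the choice until data are in hand is what a written definition should prevent.

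Several stronger readings are tempting and are not supported:

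- A reader might infer that the outcome cannot differ between arms on any interpretation. That holds only when each patient is counted once. Readings 2 and 4 can differ, but they measure something else.
- A reader might infer that the plan treats avoiding admission as a main route of benefit. Section 8.2 speaks of optimising resources, independence and quality of life; it does not mention admission avoidance.
- A reader might see the same defect in section 3.2: "Obtain the rate readmission to emergency room and hospitalization in frail older patients treated in high risk settings". That objective concerns readmission and contains no faulty ratio.

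One objection stands and shapes the remedy. The documents do not say that emergency-room participants are randomised before the decision to admit. Section 8.1 has controls assessed at admission and at discharge, with no exception for this setting. If enrolment follows that decision, admissions over randomised participants would also be close to 1 in both arms.

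**Conclusion.** The point holds. As worded, the outcome equals 1 in each arm when patients are counted once. Otherwise it duplicates readmission, leaves the randomised groups, or tracks recruitment mix. It is a wrongly stated rule that no other section corrects.

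The loss is the whole between-arm difference in admission risk: about 10 points under assumed risks of 40% versus 30%, and about 15 points under 60% versus 45%. These sizes rest on assumed risks, full recruitment of 155 per arm, and randomisation before the admission decision. The algebraic result needs only the once-per-patient count.

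This is one secondary outcome in one setting. It does not enter the sample size or affect the primary outcomes, so it should be corrected before analysis but does not threaten the trial as a whole.

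**What to change.** In section 4.2, define the outcome as the number of participants randomised in the emergency-room setting who are admitted to hospital from the index visit, divided by all participants randomised in that setting, reported by arm. Keep later admissions under the readmission outcome.

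State in the same place that randomisation precedes the admission decision. If it does not, drop the outcome or replace it with hospitalisation during follow-up per randomised participant, which the calls in 9.3 and 9.4 already collect. That version needs a stated time window, because section 7.2 gives follow-up at months 3 and 6 while 9.3 and 9.4 give months 3 and 12.

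The cost is one sentence plus one check. The denominator comes from the randomisation records. The numerator should be obtainable from the Hospital Admissions service, which section 4.2 already uses for length of stay and readmissions, or from the ward-change and discharge-destination items in 9.2. None of these explicitly records admission from the emergency room, so the sponsor should confirm that it can be extracted.
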